Our secondary aim is to determine whether the intervention affects 1) the frequency of positive-urine tests for opioids and 2) the frequency and proportion of subjects self-reporting opioid use. (We recognize that, due to constraints on in-person follow-up imposed by the COVID-19 pandemic, individuals who are most likely to get urine tests are those who are in treatment and those who might subsequently present to the emergency department (ED) for opioid-related complaints.) Our hypothesis is that our intervention will decrease both. As in the previous aim, data will be collected remotely/electronically from self-report and EPIC. If the sources of information were to conflict, then what is entered in EPIC will take precedence.

Data from our entire cohort will be compared in aggregate with patients who were started on BUP in the ED over the same time period and with historic controls who received only printed resources addressing OUD as reported in [name] et al.¹¹

2. Probable Duration of Project: State the expected duration of the project, including all follow-up and data analysis activities.

The probable duration of the project is 2 years (from 09/2019-09/2021). There is potential for extension after this time, depending on availability of funding.

3. Background: Describe the background information that led to the plan for this project. Provide references to support the expectation of obtaining useful scientific data.

Importance of problem.

The epidemic of opioid use disorder (OUD) prompted a presidential declaration of a public health emergency in October, 2017, and it was extended in January, 2018.² In 2016, an unprecedented 63,632 deaths in the United States (US) were attributed to drug overdose; 2/3 of these involved opioids.³ The deaths due to drug overdose in 2016⁴ exceeded the number of traffic fatalities during the peak year of 1972,⁵ the number of HIV deaths at their peak in 1995, the final year before the introduction of triple antiviral therapy,⁶ and the peak year for gun violence in the US, which was 1993.^{7,8} Nonfatal opioid overdoses are highly associated with ongoing OUD and recurrent overdoses. One study reviewing emergency medical service (EMS) records of

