After resuscitation from opioid overdose by naloxone, affected individuals in the EDs at the York St. and Chapel St. campuses of YNHH will be screened for OUD using a MINI. As noted above, this is an evidence-supported, standard practice at our institution. Upon screening positive for OUD, individuals should be offered BUP treatment by staff. Those who screen positive for OUD, but who decline BUP, are offered overdose and naloxone kits. In addition, by using EPIC from the Department of Emergency Medicine / EMS

[figure not shown]
offices at [name], our study team will screen for resuscitated, OUD-positive individuals, who refused BUP, if offered, and may approach these individuals in the ED to ask whether they might be interested in research participation. To be clear, due to limitations imposed by the coronavirus pandemic of 2020, as of 06/02/2020 our team will screen for prospective participants from the office at [name] and will only enter the ED to consent potentially eligible participants in person. If the prospective subject were to express interest in study participation, then the study team members would set up an appointment to meet remotely (by EPIC telehealth functions (if applicable), phone, Zoom 5.0, or other encrypted, HIPAA-compliant electronic modality) at a time of the prospective participant's choosing. Informed consent may be obtained by the RCP team in the ED or at the first electronic visit, although the latter is more likely given the constraints of ED accessibility at this time. In addition, ED providers and affiliates from AMR, staff from CCAR, Project ASSERT, Elm City Communications, and the Community Health Care Van may refer interested individuals to study participation, providing that at some time in the previous 7 days the prospective participant overdosed on opioids, were resuscitated by naloxone, and screened positive for OUD..

The RCP team will respect all safety precautions, especially those pertaining to the coronavirus pandemic, at all times. The team will respect social distancing and will don face coverings when using the office at [name]. Personal protective equipment (PPE)—masks, gloves, gowns, and sanitizers as required by ED protocol—will be worn whenever appropriate.. All individuals who might work in the ED will undergo training in proper use, including donning and doffing the designated PPE.

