Consent may be obtained at the ED, during community outreach events, electronically in a Yale School of Medicine version of REDCap®, or remotely (e.g., via email or picture), in accordance with University guidelines issued on 05/21/2020 from the Yale Center for Clinical Investigation. After consent and study initiation, either at the hospital or at some other time, the RCP team will perform a BNI—whose goal is to employ motivational techniques to help those with substance abuse consider their reasons for wanting to address dependency. Electronically, the RCP team will perform psychosocial and medical evaluations. (Please see the document, *Survey Tool and Handbook*, for details. It is included in our submission materials.) The RCP team will enter all data into a secured, encrypted database, REDCap®. To obtain consent or approximately 30 days after consent, the RCP team will schedule an electronic/remote (including by phone) Meeting 1 with participants. During this time, by remote interventions, the RCP team will collect and enter data into REDCap® based on discussions with and evaluations of participants. During an electronic/remote (including by phone) Meeting 2, which should occur no more than 180 days after consent, the RCP team will also collect and enter data into REDCap® based on discussions with and evaluations of participants. The study team will also enter data from participants' medical records at all time intervals. It is important to underscore that, due to the coronavirus pandemic, electronic and remote (including by phone) modalities will be utilized to the greatest extent possible.

Data from the entire cohort will be compared in aggregate with patients who were started on BUP in the ED over the same time period and with historic controls.¹¹

Figure 1. Screening + Enrollment

Genetic Testing N/A

A. Describe

- i. the types of future research to be conducted using the materials, specifying if immortalization of cell lines, whole exome or genome sequencing, genome wide association studies, or animal studies are planned *Write here*
 - ii. the plan for the collection of material or the conditions under which material will be received *Write here*
 - iii. the types of information about the donor/individual contributors that will be entered into a database *Write here*
 - iv. the methods to uphold confidentiality *Write here*

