3. Screen positive for OUD using mini international neuropsychiatric interview (MINI) (if applicable)	+	-
4. At least 1 opioid overdose requiring resuscitation by naloxone	+	-
5. Have a non-opioid overdose explanation for decreased level of consciousness, miosis, or decreased respiratory rate (if applicable)	-	+
6. Positive for OUD using a health questionnaire containing questions about prescription opioid and heroin use	+	-
7. Not in a critically ill state at the time of consent (e.g., not actively suicidal, psychotic, septic, and/or experiencing cardiac arrest)	+	-
8. 3.,4., & 6. (in this column) must have occurred within ≤ 7 days (inclusive) from date of consent if the prospective participant were immediately discharged from the emergency department (ED), floor, or other health care facility; consent may be obtained at any of these locations	+	-
9. Homicidal	-	+
10. Able to consent to program/study participation	+	-
11. Permanent residence is a long-term care/skilled nursing facility	-	+
12. Simultaneously enrolled in another study whose principal investigator (PI) or co-PI is a faculty member in the Department of Emergency Medicine	-	+
13. Prescribed opioids for acute pain, chronic pain, or palliative care without OUD	-	+
14. Stably enrolled in opioid agonist treatment or other medication-assisted therapy for OUD at the time of consent	-	+
15. In police custody or incarcerated (at the time of consent to participate or any known time after). (Parolees & those on probation may be eligible, but are NOT the target population and may be enrolled only incidentally .)	-	+
16. Refused buprenorphine/naloxone (BUP), if offered	+	-
17. Has a mailing address or P.O. box	+	-
18. Able to answer questions electronically/remotely (including by phone)	+	-

8. How will **eligibility** be determined, and by whom? *Write here*

In general, eligibility will be determined by the RCP team. ED and study staff may assist occasionally.

9. **Risks:** Describe the reasonably foreseeable risks, including risks to subject privacy, discomforts, or inconveniences associated with subjects participating in the research.

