
- d. For multi-site studies for which the Yale PI serves as the lead investigator: N/A
 - i. How will adverse events and unanticipated problems involving risks to subjects or others be reported, reviewed and managed? N/A
 - ii. What provisions are in place for management of interim results? N/A
 - iii. What will the multi-site process be for protocol modifications? N/A

12. **Statistical Considerations:** Describe the statistical analyses that support the study design.

Study design

Primary outcomes

The primary outcomes will be 1) percentage of individuals with repeat opioid overdose events requiring naloxone resuscitation, identified using YNHH's electronic medical record system (EPIC), and 2) percentage of individuals engaged in any treatment for OUD or who are in remission. Data will be recorded at baseline and at 30 and 180 days after consent to participate in the research.

Secondary outcomes

The secondary outcomes will be 1) frequency and percentage of individuals with positive opioid tests (urine) recorded in their hospital charts or during medication program monitoring, and 2) frequency and percentage of subjects with self-reported opioid use. Data will be recorded at baseline and at 30 and 180 days after consent to participate in the research.

Statistical analyses

We will document demographics (sex, race/ethnicity, age, education, employment status, etc.) and clinical characteristics (e.g., heroin use, non-opioid use in the past 6 months, lifetime treatment for addiction etc.) among all cohorts. χ^2 tests (2 df) will be employed to detect statistically significant differences.

Group	X	No X	Total
PRIDE + CCAR intervention			
BUP-initiated in ED after OD			
Historical control(s)			
Total			

For primary outcomes, "X" is % of repeated overdose events or % of treatment engagement. For secondary outcomes, "X" is frequency or % positive testing for opioid tests or % (self-reported) opioid abuse.

Sample size determination

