Our research is funded by an R01 through the CDC, which no longer issues hardcopy Certificates of Confidentiality (CoCs). However, as noted above, per section 2012 of the 21st Century Cures Act, a CoC "automatically" has been issued by the agency.

<https://www.cdc.gov/od/science/integrity/confidentiality/applinst.htm>

SECTION V: POTENTIAL BENEFITS

Potential Benefits: Identify any benefits that may be reasonably expected to result from the research, either to the subject(s) or to society at large. (Payment of subjects is not considered a benefit in this context of the risk benefit assessment.)

Participants are expected to directly benefit from the educational, counseling, and medical resources and contacts. We expect that this will provide better outcomes in the short- and possibly long-terms.

SECTION VI: RESEARCH ALTERNATIVES AND ECONOMIC CONSIDERATIONS

1. **Alternatives:** What other alternatives are available to the study subjects outside of the research? Participants may decline study participation or participate in another study. BUP can be started in the ED for individuals willing to accept it at the time of an OD. Other resources for harm reduction and treatment are routinely provided at the time of an ED visit, but are seldom associated with positive short-term outcomes.

2. **Payments for Participation (Economic Considerations):** Describe any payments that will be made to subjects, the amount and schedule of payments, and the conditions for receiving this compensation.
Participants will receive 3 payments of \$25 (for a total of \$75) after consent and after the first and second meetings. Each payment is given as a \$25 gift card to Stop & Shop. Initial payments may be obtained upon consent in the ED; subsequent payments will be mailed or provided electronically, according to subjects' preferences.
3. **Costs for Participation (Economic Considerations):** Clearly describe the subject's costs associated with participation in the research, and the interventions or procedures of the study that will be provided at no cost to subjects.
The research will not generate any costs to participants, as we expect that study personnel will meet with them at settings and times of participants' choosing and convenience. All medical and laboratory testing is part of participants' routine care and is not directly a feature of the research itself. Additionally, for those electing to receive BUP, grant funding will cover its cost.

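### The address and remote-contact criteria restrict the RCP cohort only; no matching condition is stated for the concurrent ED-started BUP group, and the crude comparison does not correct for it

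*Combined protocol and SAP*

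**What the plan says.** **RCP entry.** In Section I, item 7 (Inclusion/Exclusion Criteria), criterion 17 reads "Has a mailing address or P.O. box" and criterion 18 reads "Able to answer questions electronically/remotely (including by phone"). Failing either one excludes. Criterion 16 limits the cohort to people who refused BUP if it was offered. Section I, item 4 (Research Plan) adds a practical step: "Informed consent may be obtained by the RCP team in the ED or at the first electronic visit, although the latter is more likely".

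**Comparators.** Section I, item 1 (the aims) names two. One is "patients who were started on BUP in the ED over the same time period". The other is "historic controls who received only printed resources addressing OUD as reported in" a cited randomised trial. The table in item 12 (Statistical Considerations) narrows the first to BUP started after an overdose. No address, phone or appointment condition is stated for that group. The entry criteria of the historical trial are not given.

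**Analysis.** Item 4 states: "Data from the entire cohort will be compared in aggregate". Item 12 states that chi-square "tests (2 df) will be employed to detect statistically significant differences", and the table beneath applies this to the outcomes. No restriction, matching, weighting or adjustment is described. The characteristics to be documented include sex, race/ethnicity, age, education and employment. The list is open-ended, but housing and contact status are not named.

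**The concern.** One row of the outcome table is filtered on having an address and being reachable, and the concurrent row, as written, is not. The protocol itself treats housing as relevant to recovery. Section I, item 3 (Background) lists a stable home among the dimensions that support recovery, gives coaches the task of linking people to sober housing, and reports housing as a worry among overdose survivors who had declined BUP. If lacking an address or remote contact goes with more repeat overdoses or less engagement, part of any RCP advantage over the concurrent group would come from the entry rule. A crude test cannot separate that part from an effect of the intervention.

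Unlike refusal of BUP, which defines the target population, criteria 17 and 18 are logistical. They can be roughly mirrored in a record-based comparator, so this imbalance is avoidable.

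**Working it through.** **What the plan offers to reproduce.** Nothing on this point. It gives no outcome rate by housing or contact status, and no share of concurrent patients who would fail criterion 17 or 18. The sample-size paragraph (about 100 people, 80% power, 5% significance) does not bear on it. What follows is an illustration on assumed inputs.

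**Assumed inputs**, with no true RCP effect:
- *u*, the share of concurrent patients who would fail criterion 17 or 18: 10–40%.
- *p*, repeat-overdose risk in people who meet both: 10–30%.
- *RR*, risk ratio for those who do not: 1.5–2.
- *q*, engagement in people who meet both: 40–60%.
- *r*, engagement ratio for those who do not: 0.5–0.75.
- 100 people per group and a two-sided 5% two-group test, in place of the plan's three-group test.

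**Formulas**
- Overdose: comparator rate = (1 − u)p + u·p·RR, so the spurious benefit is u·p·(RR − 1).
- Engagement: comparator rate = (1 − u)q + u·q·r, so the spurious benefit is u·q·(1 − r).
- Chance of a false significant result in favour of RCP = Φ[(d − 1.96·SE₀)/SE₁], where d is the spurious difference, SE₀ its pooled and SE₁ its unpooled standard error.

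**Results**

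| Outcome | Case | RCP | Comparator | Spurious benefit | False result for RCP |
|---|---|---|---|---|---|
| Overdose | p = 10%, u = 10%, RR = 1.5 | 10% | 10.5% | 0.5 points | 3.3% |
| Overdose | p = 20%, u = 20%, RR = 2 | 20% | 24% | 4 points | about 10% |
| Overdose | p = 30%, u = 40%, RR = 2 | 30% | 42% | 12 points | 42% |
| Engagement | q = 40%, u = 10%, r = 0.75 | 40% | 39% | 1 point | 3.5% |
| Engagement | q = 50%, u = 20%, r = 0.5 | 50% | 45% | 5 points | 10.5% |
| Engagement | q = 60%, u = 40%, r = 0.5 | 60% | 48% | 12 points | 40% |

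The middle overdose case in full: SE₀ = √(2 × 0.22 × 0.78/100) = 0.0586; SE₁ = √[(0.20 × 0.80 + 0.24 × 0.76)/100] = 0.0585; (0.04 − 1.96 × 0.0586)/0.0585 = −1.28; Φ(−1.28) is about 0.10. Without bias the figure is 2.5%. If RR = 1, r = 1 or u = 0, the bias is zero.

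**The opposing component.** Item 3 (Background) says that fewer than half of those who start BUP remain engaged, roughly double the proportion with a brief interview or referral only. If 30–50% of starters stay engaged (assumed), half of that is 15–25%, and the gap is 15 to 25 points. For a cohort of refusers set against starters, with no RCP effect, a gap of that order would count against RCP on engagement. It exceeds the 1 to 12 points above. The ratio mixes the effect of BUP with differences between patients, so it is a rough gauge only.

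**The case against.** The strongest reply is that the eligibility filter is minor beside the difference between refusers and acceptors, and that the two may pull in opposite directions. The Background also associates BUP with a lower overdose risk, so the pull against RCP need not be confined to engagement. In addition, repeat overdoses are identified in EPIC. Events among mobile comparator patients treated elsewhere could be missed, which would again work against RCP. This stands. A reader might infer that RCP will look better than it is overall, but the documents do not support that.

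Two other readings also go too far.
- *That the criteria shut out unhoused people.* Any mailing address or a P.O. box satisfies 17, and a phone satisfies 18. Referrals are taken from the Housing Authority and the Community Health Care Van, and consent may be given in the ED or the community. Only people with no mailing address at all, or no remote contact, are excluded.
- *That neither comparator has such a filter.* For the concurrent group, all that can be said is that none is stated. The historical trial may have had its own contact requirement, and the documents do not say.

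The housing evidence is also weaker than it looks. It comes from a purposive sample of 16 overdose survivors, drawn to understand why people decline BUP. It does not show how common lack of an address or phone is among those who start BUP.

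None of this removes the point. Biases of unknown size do not cancel by design, and this one can be reduced cheaply.

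**Conclusion.** As written, criteria 17 and 18 apply to RCP alone, no counterpart is stated for the concurrent group, and the planned test does not correct for the imbalance. If people without an address or remote contact do worse, this is one bias component that probably favours RCP. Its true size is unknown. The illustrated 0.5 to 12 points (overdose) and 1 to 12 points (engagement) rest wholly on the assumed shares, rates and ratios. The net direction of bias in the comparison with the concurrent group is undetermined, and the documents do not allow the comparison with the historical arm to be assessed on this point. The change is worth making because the imbalance is avoidable, not because a net advantage to RCP has been shown.

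**What to change.** 1. **Define the concurrent cohort in Section I, item 12** by the same entry criteria that EPIC can show at the index visit. Examples are age, an overdose treated with naloxone, not living in a long-term care facility, not already stably on medication-assisted treatment before that visit, and an address and phone number on file as a proxy for 17 and 18. List the criteria that cannot be applied. The documents do not show, for instance, that EPIC can identify homicidality or enrolment in another departmental study.
2. **Report how many concurrent patients the address and phone filter removes, and their outcomes.** This replaces the assumed *u*, *RR* and *r* with data.
3. **State that the historical arm cannot be aligned in this way.**
4. **Treat criterion 17 the same in both groups.** Contact and consent can be electronic, and Section VI, item 2 says "subsequent payments will be mailed or provided electronically", so dropping it is possible, but that is a design preference. If it is dropped for RCP, the address filter must be dropped for the comparator too, or the imbalance returns in reverse.
5. **State the limits that remain:** the refuser-versus-acceptor difference, and the remote consent appointment, which has no counterpart in the comparator.

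The cost is one filter in the EPIC extract and a short amendment to item 12. The concurrent cohort becomes somewhat smaller. The proxy is imperfect, since an address or number on file may be out of date and does not prove that a person can be reached.

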Our principal aim is to determine whether a novel biopsychosocial intervention following opioid overdose (OD) affects 1) the frequency of secondary opioid OD events and 2) the proportion of individuals who remain engaged in treatment for opioid use disorder (OUD) or are in remission at 30 days and at 180 days post consent. We define remission as engagement in daily medication-assisted therapy (MAT)—typically buprenorphine/naloxone (BUP) or methadone—and/or a recovery capital score of ≥ 27.5 .¹ Our intervention will connect individuals with important community resources that hopefully will facilitate progress toward long-term recovery. Specifically, we will link individuals with moderate-severe OUD, who have experienced at least 1 opioid OD requiring naloxone resuscitation but refused BUP treatment, if offered, with 1) treatment with BUP, 2) methadone maintenance, intensive outpatient, or residential treatments, or 3) education materials from the Connecticut Community for Addiction Recovery (CCAR). Enrolled participants may switch from 1)-3) throughout. To carry out the intervention, an addiction recovery coach from CCAR and a health educator (research) paramedic will form a team (RCP team) and perform remote (including over-the-phone) and/or electronic follow-up visits after a participant has experienced at least 1 opioid OD requiring naloxone resuscitation. Our hypothesis is that the intervention, by the RCP team, connecting participants to community resources will decrease subsequent OD events and increase the likelihood of remission. To evaluate this hypothesis, data will be collected from self-report and from EPIC, Yale New Haven Hospital's (YNHH) medical record system. If the sources of information appear to conflict, then what is entered in EPIC will take precedence.

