164 persons with fatal opioid overdose found that 62% had been treated for at least one previous overdose, while 17% had 3 or more prior overdoses.⁹ In another large study involving a single health system, nearly 10% of patients presenting with nonfatal drug overdoses were deceased within 12 months, though not all deaths were due to fatal overdoses.¹⁰ Their findings in that study reflect some of the changing demographics of OUD, as multi-variate analysis showed increased age, comorbidities such as cancer and end-stage renal disease, and polypharmacy correlated with the highest 1-year mortality.

Scientific premise for proposed project.

Buprenorphine/naloxone-based (BUP) treatment for OUD.

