Some small studies and anecdotal successes have been reported in a variety of settings when community paramedics were included in programs to assist patients with OUD. However, there have been no formal studies about the various possible roles of the paramedics or clinical outcomes. Most of the available reports are in EMS trade journals, organization newsletters, public news releases, and other "gray" literature. For example, a Fairfield County, Ohio initiative called Project Fairfield Overdose Response Team (FORT), dispatches a community paramedic and a law enforcement officer to meet with patients after opioid overdoses. This is a community outreach model program that contacts patients, within 1-3 days of overdose, and assists them with getting into treatment facilities, which are aimed primarily at abstinence. With no reports of formal outcomes, as of December, 2017, Project FORT had piloted 12 patients. Of these, 1 was known to be in an inpatient treatment program, and another had been admitted to the hospital for opioid withdrawal then discharged to inpatient treatment.²⁵ The Johns Hopkins Bloomberg School of Public Health is collaborating with Baltimore City Fire Department's paramedics and the Behavioral Health System of Baltimore in a program that trains the paramedics to perform a screening test for OUD, followed by a BNI after responding to opioid overdoses. At the time of their report, patients with OUD were being referred by the paramedics to a community-based research center within the Bloomberg School for counseling, motivation, and discussion of barriers to treatment. HIV (+) patients were preferentially referred to a medical facility for treatment with BUP along with management of their HIV disease. Their longer-term plan was to eventually transport clinically stable patients after overdose directly to a sobering center, similar to the protocol used in the City of San Francisco.²⁶ Although the patients referred by the paramedics to the community-based research center are randomized to one of 2 different treatment arms, there have been no reports of the effectiveness of the paramedics in this role. In a Palm Beach, FL community paramedicine program loosely based on previous work at Yale, consenting patients are started on BUP in the ED after an overdose. But community paramedics deliver the ensuing daily doses to the patients at home for the first week of therapy. These medics are accompanied by peer recovery specialists who work with the patient on support systems for longer term recovery. Although no outcomes data are available for this program, it involves a rapid taper off of BUP early in the treatment regimen. In most other studies, early discontinuation of BUP is associated with poorer short- and long-term outcomes, and increased risk of nonfatal and fatal overdoses.

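### Primary outcome 1 is narrower than Aim 1 and, on its plain reading, does not count a fatal opioid overdose that has no recorded naloxone resuscitation.

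*Combined protocol and SAP*

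**What the plan says.** - **Aim.** The principal aim at the start of Section I asks whether the intervention affects "the frequency of secondary opioid OD events". Section I, 4 (Research Plan) repeats this. Neither statement attaches a naloxone condition to the secondary event. For the two principal-aim outcomes together, the opening section says "data will be collected from self-report and from EPIC", and that EPIC prevails if the sources conflict.
- **Outcome.** Section I, 12 (Primary outcomes) makes primary outcome 1 the "percentage of individuals with repeat opioid overdose events requiring naloxone resuscitation" and names EPIC as the means of identification. Data are recorded at baseline and at 30 and 180 days after consent.
- **Analysis table.** Each cohort is split into X and No X. The footnote says that for primary outcomes X "is % of repeated overdose events or % of treatment engagement".
- **Death.** Participant death appears only as a criterion for a serious adverse event (Section I, 11). No section says whether a fatal overdose without recorded resuscitation is X, No X or excluded.
- **Background mortality.** Section I, 3 cites one health system in which "nearly 10% of patients presenting with nonfatal drug overdoses were deceased within 12 months, though not all deaths were due to fatal overdoses".

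**The concern.** A fatal opioid overdose is the worst form of the event that the intervention is meant to prevent. If the person was found dead, or no resuscitation was recorded, the wording of Section 12 does not make that death an event. The table has only two columns, so the person most naturally lands in No X, beside participants who had no overdose at all.

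Two things are at stake. The efficacy rate for a primary outcome could be understated by its most serious events. And because no rule is written, the decision on how to count such a death could be taken after the data are known.

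Safety oversight is not affected: a death meets the serious adverse event definition and is reviewed as such. The gap concerns the efficacy rate only.

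**Working it through.** **Text, side by side**

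| | Aim 1 | Primary outcome 1 |
|---|---|---|
| Event | any secondary opioid overdose | repeat opioid overdose requiring naloxone resuscitation |
| Measure | frequency | percentage of individuals |
| Source | self-report and EPIC, stated for the aim as a whole | EPIC |
| Fatal overdose | not mentioned; within the wording | not mentioned; outside the plain wording if no resuscitation was recorded |

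**Size.** The plan gives no rate for repeat or fatal overdose, so there is no figure to reproduce. What follows is illustrative.

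Inputs:
- mortality of 10% at 12 months, rounding the cited figure (Section I, 3)
- follow-up to days 30 and 180 (Section I, 12)
- 100 participants (Section III, 1)
- assumed: constant hazard; 25% to 75% of deaths due to opioid overdose

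1. Deaths from any cause:
   - day 30: 1 − 0.9^(30/365) = 0.0086, or 0.9 per 100
   - day 180: 1 − 0.9^(180/365) = 0.0506, or 5.1 per 100
2. Overdose deaths by day 180: 0.25 × 5.06 = 1.27 and 0.75 × 5.06 = 3.80 per 100.
3. Effect on the day-180 rate: 0 points if every fatal overdose had a recorded resuscitation or followed an event already counted; 3.8 points if the share is 75% and none is otherwise counted. Counting every death, including those of unknown cause, adds at most 5.1 points.
4. Effect of the counting rule alone. Suppose 20% have a non-fatal repeat overdose and a further 2.5% have an uncounted fatal one (both assumed). The outcome is 22.5% if the deaths are X, 20% if they are No X, and 0.20 / 0.975 = 20.5% if they are excluded.
5. Chance that at least one uncounted fatal overdose occurs among 100 participants. Let q be the share of overdose deaths with neither a recorded resuscitation nor an earlier counted event. The documents do not give q. The chance is 1 − (1 − q × d)^100, with d = 0.0127 to 0.0380:

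| q (assumed) | q × d | Chance of at least one |
|---|---|---|
| 0.25 | 0.0032 to 0.0095 | 27% to 61% |
| 0.50 | 0.0063 to 0.0190 | 47% to 85% |
| 1 (maximum) | 0.0127 to 0.0380 | 72% to 98% |

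6. Sensitivity to mortality. At half the cited figure, 1 − 0.95^(180/365) = 0.0250. Overdose deaths are then 0.6 to 1.9 per 100, and the maximum chance (q = 1) falls to 47% to 85%.

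**The case against.** **Only one operational definition exists.** Section 12 is the only place headed as primary outcomes, and aims are usually worded more broadly. A reader might infer that the aim, the outcome and the footnote are three rival definitions. The footnote does not support that: the same line shortens primary outcome 2 to treatment engagement and drops remission, so it is probably shorthand. This stands. The mismatch is between Aim 1 and Section 12.

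**Self-report is not clearly a rival source for overdose.** The sentence on data sources follows a hypothesis covering both overdose and remission, and remission can rest on an interview score. Section 12 assigns EPIC to overdose. This stands too.

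***Requiring* is not *receiving*.** A fatal opioid overdose can be said to have required resuscitation that did not come. That reading is open, so the documents do not support a flat statement that such deaths are excluded. Nor do they adopt the looser reading, and placing the death in No X is an inference from a two-column table. The ambiguity is what needs settling.

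**The mortality figure is a loose guide.** It covers all causes and any drug in another health system, where "increased age, comorbidities such as cancer and end-stage renal disease, and polypharmacy correlated with the highest 1-year mortality". The overdose share has no basis in the documents. Both points stand, which is why the size is given as a range from zero.

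**The Background mention of "increased risk of nonfatal and fatal overdoses" concerns early discontinuation of buprenorphine/naloxone in other studies.** It does not define this trial's endpoint, and nothing here rests on it.

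**The naloxone condition is reasonable.** It mirrors the entry criterion and can be checked in the chart. For non-fatal events that is a sound reason to keep it. It does not answer the case of a person who died without recorded resuscitation.

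**Conclusion.** The point holds in a limited form. Primary outcome 1 is narrower than Aim 1, and on its plain reading a fatal opioid overdose without recorded resuscitation is not an event. Naming fatal overdose as an event changes the definition for the better, beyond filling in a missing detail.

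The effect on the day-180 rate is 0 to 3.8 points. That rests on the cited mortality, a constant hazard and an assumed overdose share of 25% to 75%.

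Two stronger conclusions are tempting and are not supported. The first is that the uncounted case has a 72% to 98% chance of arising. That range is the chance of any overdose death, and it applies to the uncounted case only if no overdose death had a recorded resuscitation or an earlier counted event. The second is that the gap favours the intervention cohort. Nothing in the documents establishes how often such deaths would occur, or be recorded, in one cohort relative to another.

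**What to change.** 1. Define primary outcome 1 as the percentage of individuals with at least one repeat opioid overdose after consent, through day 30 and through day 180, that is either (a) non-fatal and requiring naloxone resuscitation, as now, or (b) fatal, with or without recorded resuscitation. Align the aim and the footnote to this, including percentage of individuals in place of frequency.
2. In between-cohort comparisons, identify fatal overdoses from the same source in each cohort compared, namely EPIC-recorded deaths. Do not add deaths known only from serious adverse event records to the intervention cohort alone. If the historical controls have no such source, do not compare them on the outcome that includes fatal events.
3. Count deaths of unknown cause as events in a sensitivity analysis.
4. Report overdose deaths known only from serious adverse event records or other sources descriptively for the intervention cohort.
5. Keep participants who die in the denominator of primary outcome 2, counted as neither engaged in treatment nor in remission.

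The cost is rewording plus limited chart review for cause of death. The reported overdose rate may be slightly less favourable. Deaths absent from EPIC would still be missed in the between-cohort comparison, and the report should say so.
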